9.6.1.4 Analysis Strategy for Key Efficacy Endpoints

Table 8 summarizes the primary analysis approach for key efficacy endpoints.

Endpoint/Variable	Statistical Method ^a	Analysis Population	Missing Data Approach		
Primary Analyses					
EFS	Testing: Stratified Log-rank Test Estimation: Stratified Cox model with Efron's tie handling method	ITT	Censored according to rules in Table 7		
Key Secondary Analyses					
OS	Testing: Stratified Log-rank Test Estimation: Stratified Cox model with Efron's tie handling method	ITT	Censored at last known alive date		
Abbreviations: EFS=event-free survival; ITT=intent to treat; OS=overall survival ^a Statistical models are described in further detail in the text. For stratified analyses, the stratification factors used for randomization (Section 6.3.2) will be applied to the analysis. Small strata will be combined in a way specified by a blinded statistician prior to the analysis.					

Table 8Efficacy Analysis Methods for Key Efficacy Endpoints

Analysis strategy for the exploratory efficacy endpoints will be described in the sSAP.

9.6.2 Statistical Methods for Safety Analyses

Safety and tolerability will be assessed by clinical review of all relevant parameters including AEs, laboratory tests, and vital signs.

The analysis of safety results will follow a tiered approach as shown in Table 9. The tiers differ with respect to the analyses that will be performed. AEs (specific terms as well as system organ class terms) and events that meet predefined limits of change (PDLCs) in laboratory, and vital signs are either prespecified as "Tier 1" endpoints or will be classified as belonging to "Tier 2" or "Tier 3" based on the observed proportions of participants with an event.

Tier 1 Events

Safety parameters or AEs of interest that are identified a priori constitute "Tier 1" safety endpoints that will be subject to inferential testing for statistical significance. There are no Tier 1 events for this protocol as SBRT+pembrolizumab does not seem to produce toxicity beyond what is expected for these therapies alone based on the early result of the use of pembrolizumab and SBRT in the metastatic setting [Theelen, W., et al 2018] [Campbell, A. M., et al 2018].

Tier 2 Events

Tier 2 parameters will be assessed via point estimates with 95% confidence intervals provided for differences in the proportion of participants with events via the Miettinen & Nurminen method [Miettinen, O. and Nurminen, M. 1985] and will be presented using forest plots.

Membership in Tier 2 requires that at least 1% of participants in any treatment group exhibit the event (with the exception of any AE, which requires at least 10%). The threshold of at least 1% of participants was chosen because the population randomized in this study is in critical condition and usually experiences various AEs of similar types regardless of treatment; events reported less frequently than 1% of participants would obscure the assessment of the overall safety profile and add little to the interpretation of potentially meaningful treatment differences. Grade 3 to 5 AEs (\geq 1% of participants in one of the treatment groups) and SAEs (\geq 1% of participants in one of the treatment groups) are considered as Tier 2 endpoints. Any AE (\geq 10% of participants in one of the treatment groups) is also considered as a Tier 2 endpoint (the cutoff 10% is chosen due to the higher incidence of any AE). Because many 95% CIs may be provided without adjustment for multiplicity, the CIs should be regarded as a helpful descriptive measure to be used in safety review rather than formal methods for assessing the statistical significance of the betweengroup differences. All other AEs and predefined limits of change will belong to Tier 3 endpoints.

Tier 3 Events

Safety endpoints that are not Tier 1 or 2 events are considered Tier 3 events. Only point estimates by treatment group are provided for Tier 3 safety parameters.

Continuous Safety Measures

For continuous measures such as changes from baseline in laboratory and vital signs, summary statistics for baseline, on-treatment, and change from baseline values will be provided by treatment group in table format.

100

Safety Tier	Safety Endpoint	95% CI for Treatment Comparison	Descriptive Statistics	
Tier 2	Any AE (≥10% of participants in one of the treatment groups)	Х	Х	
	Any SAE (≥1% of participants in one of the treatment groups)	Х	Х	
	Any Grade 3 to 5 AE (≥1% of participants in one of the treatment groups)	Х	Х	
Tier 3	Other specific AEs, SOCs or PDLCs		Х	
	Change from baseline results (laboratory test results, vital signs)		Х	
Abbreviations: AE=adverse event; CI=confidence interval; PDLC=predefined limit of change; SAE=serious adverse event; SOC=system organ class; X=results will be provided.				

 Table 9
 Analysis Strategy for Safety Parameters

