6.6 Dose Modification (Escalation/Titration/Other)

Pembrolizumab dose reductions are not permitted. Pembrolizumab treatment may be interrupted or discontinued due to toxicity. Pembrolizumab may be interrupted for a maximum of 12 weeks. An interruption of study intervention for more than 12 weeks will require Sponsor approval before treatment can be resumed (see Section 6.4). See Appendix 7 for country-specific dose modification requirements.

If radiotherapy is not completed for any reason, the participant may continue with pembrolizumab/placebo for up to 17 total treatment cycles (1 year). If SBRT is interrupted due to toxicity, all fractions of radiotherapy must be completed prior to Cycle 2 Day 1 of pembrolizumab/placebo (day second dose is administered) or SBRT must be discontinued early. Should the participant develop radiation pneumonitis, refer to Table 4 to follow the same management guidelines for irAE pneumonitis, specifically with action taken for study intervention, and treat as per local SOC.

Dose Modification and Toxicity Management for Immune-related AEs Associated With Pembrolizumab

AEs associated with pembrolizumab exposure may represent an immune-related response. These irAEs may occur shortly after the first dose or several months after the last dose of pembrolizumab treatment and may affect more than one body system simultaneously. Therefore, early recognition and initiation of treatment is critical to reduce complications. Based on existing clinical study data, most irAEs were reversible and could be managed with interruptions of pembrolizumab, administration of corticosteroids, and/or other supportive care. For suspected irAEs, ensure adequate evaluation to confirm etiology or exclude other causes. Additional procedures or tests such as bronchoscopy, endoscopy, skin biopsy may be included as part of the evaluation.

Based on the severity of irAEs, withhold or permanently discontinue pembrolizumab and administer corticosteroids.

Dose Modification and Toxicity Management Guidelines for irAEs Associated With Pembrolizumab Monotherapy, Coformulations, or IO Combinations are provided in Table 4.

Table 4Dose Modification and Toxicity Management Guidelines for Immune-relatedAdverse Events Associated with Pembrolizumab Monotherapy, Coformulations or IOCombinations

General instructions:

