- The participant's treatment assignment has been intentionally unblinded by the investigator, MSD subsidiary, or through the emergency unblinding call center. Note: if a participant's treatment is unintentionally unblinded, the participant is not required to discontinue treatment.

- Any prolonged interruption of study intervention beyond the permitted periods, for irAE management or other allowed dose interruptions, as noted in Section 6.6, require Sponsor consultation prior to restarting treatment. If treatment will not be restarted, the participant will continue to be monitored in the study and the reason for discontinuation of study intervention will be recorded in the medical record.
- The participant has a medical condition or personal circumstance which, in the opinion of the investigator and/or Sponsor, places the participant at unnecessary risk from continued administration of study intervention.
- Pathological recurrence of disease or radiographic recurrence of disease outlined in Section 8.2.1.3. If the radiographic recurrence is biopsied and the pathology is negative, the patient may continue treatment until pathological or radiographic confirmation of recurrence by repeat imaging or biopsy.
- The participant has a confirmed positive serum pregnancy test.
- Completion of 17 doses (approximately 1 year) of pembrolizumab/placebo.
- Prohibited concomitant therapy or vaccinations as defined in Section 6.5 are administered during the study.
- Recurrent Grade 2, Grade 3, or Grade 4 pneumonitis of any cause and Grade 3 colitis.
- Any progression or recurrence of any malignancy, or any occurrence of another malignancy that requires active treatment.
- Any study intervention-related toxicity specified as a reason for permanent discontinuation as defined in the guidelines for dose modification due to AEs in Section 6.6.

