8.1.8.1 Timing of Dose Administration

8.1.8.1.1 Pembrolizumab or Matching Placebo

Pembrolizumab will be administered as a dose of 200 mg using a 30-minute IV infusion Q3W. Sites should make every effort to target infusion timing to be as close to 30 minutes as possible. However, given the variability of infusion pumps from site to site, a window of -5 minutes and +10 minutes is permitted (ie, infusion time is 30 minutes -5 min/+10 min).

The Pharmacy Manual contains specific instructions for pembrolizumab reconstitution, preparation of the infusion fluid, and administration of infusion solution. Pembrolizumab will be prepared by the unblinded pharmacist and will be dispensed by the blinded pharmacist and administered by blinded and qualified trial site personnel.

The placebo will be a normal saline solution prepared by the unblinded pharmacist. The placebo will be dispensed by the blinded pharmacist and administered by blinded and

qualified trial site personnel in the same manner as the investigational product (pembrolizumab).

The first dose of pembrolizumab or placebo should be administered prior to start of SBRT.

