9.5.2 Safety Analysis Populations

The APaT population will be used for the analysis of safety data in this study. The APaT population consists of all randomized participants who received at least 1 dose of study intervention. Participants will be included in the treatment group corresponding to the study intervention they actually received for the analysis of safety data using the APaT population. This will be the treatment group to which they are randomized except for participants who take incorrect study intervention for the entire treatment period; such participants will be included in the treatment group corresponding to the study intervention actually received.

At least 1 laboratory or vital sign obtained after at least 1 dose of study intervention is required for inclusion in the analysis of the respective safety parameter. To assess change from baseline, a baseline measurement is also required.

Details on the approach to handling safety analyses are provided in Section 9.6.2.

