9.6 Statistical Methods

NOTE: As of Amendment 08, all the prespecified interim analyses after IA1 and final analysis of the study described in the SAP will not be performed. Safety analysis will be performed at the end of the study; there will be no further pre-planned analyses for efficacy and ePRO endpoints collected from participants beyond the IA1 cutoff date of 11-JUN-2024. The subsections below are retained for reference.

This section describes the statistical methods that address the primary and secondary objectives. Methods related to exploratory objectives will be described in the sSAP. Efficacy results that will be deemed to be statistically significant after consideration of the Type I error control strategy are described in Section 9.8. Nominal p-values will be computed for other efficacy analyses but should be interpreted with caution due to potential issues of multiplicity. If there are a small number of events in one or more strata, for the purpose of analysis, strata will be combined to ensure sufficient number of events in each stratum. Details regarding the combining of strata will be specified in the sSAP prior to database lock based on a blinded review of response counts by stratum.

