9.8.1.2 Overall Survival

9.9 Sample Size and Power Calculations

NOTE: As of Amendment 08, all the prespecified interim analyses after IA1 and final analysis of the study described in the SAP will not be performed. This section is retained for reference.

The sample size is estimated based on the secondary endpoint OS.

A total of approximately 436 participants will be randomized in a 1:1 ratio to the SBRT + pembrolizumab arm and the SBRT + placebo arm.

Confidential

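### Section 9.6.2 prespecifies no pooled pneumonitis comparison: any-grade terms below 10% get per-arm rates only, and severe cases are compared term by term

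*Combined protocol and SAP*

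**What the plan says.** Section 9.6.2 sorts safety parameters into three tiers.

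- **Tier 1** (significance testing) is empty: "There are no Tier 1 events for this protocol as SBRT+pembrolizumab does not seem to produce toxicity beyond what is expected for these therapies alone".
- **Tier 2** gives a difference in proportions with a Miettinen-Nurminen 95% CI. Entry needs at least 10% in one arm for an adverse event of any grade, and at least 1% in one arm for a serious or a Grade 3 to 5 event.
- **Tier 3** gives a percentage per arm and nothing else: "All other AEs and predefined limits of change will belong to Tier 3 endpoints".

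The units that are tiered are specific adverse event terms and system organ classes. No grouped pneumonitis category is defined, and the events of clinical interest in Section 8.4.7 are an overdose and a liver-test criterion.

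Elsewhere the protocol joins the causes. Section 6.6 states: "Should the participant develop radiation pneumonitis, refer to Table 4 to follow the same management guidelines for irAE pneumonitis". Section 6.5 makes the same link for steroid use. Section 7.1 lists as a reason for discontinuing study intervention: "Recurrent Grade 2, Grade 3, or Grade 4 pneumonitis of any cause".

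Under Amendment 08 this analysis still stands: "Safety analysis will be performed at the end of the study". It uses the all-participants-as-treated (APaT) set of Section 9.5.2: "The APaT population consists of all randomized participants who received at least 1 dose of study intervention".

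**The concern.** Safety and tolerability of the combination is a secondary objective, and both components can cause lung inflammation. In clinical handling, the protocol does not ask which component was responsible. In the analysis, the answer may decide the row. Section 10.3.5 asks investigators to record a diagnosis, so the reported term can follow the presumed cause. Independent adjudication of pneumonitis is required only in Japan (Section 10.7.4).

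Two things follow. Lower-grade cases divided between terms can leave each term under 10%, so that neither has a planned difference or CI. And no row counts a participant once across terms, so the total burden of pneumonitis in each arm cannot be read from the tables. Lower-grade events are not trivial here: in Table 4, Grade 2 pneumonitis already leads to withholding of treatment.

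At stake is how clearly the final report describes the lung toxicity added by pembrolizumab. No efficacy conclusion and no error rate is affected.

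**Working it through.** The plan gives no figure to reproduce; the point rests on a reporting rule. The check turns the cut-offs into counts, finds how often a term would miss them, and shows what pooling could add.

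**Inputs**
- Size, from Section 9.9: "A total of approximately 436 participants will be randomized in a 1:1 ratio". 436 / 2 = 218 per arm. The number dosed is not given, so 218 is an assumption for the APaT set.
- Cut-offs of 10% and 1%, from Section 9.6.2 and Table 9.
- Pneumonitis rates by arm are not in the documents. All rates and counts below are assumed.

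**1. Cut-offs as counts.** 0.10 × 218 = 21.8, so 22 participants. 0.01 × 218 = 2.18, so 3 participants. At 200 per arm they would be 20 and 2.

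**2. Chance that a term gets no between-arm CI.** With independent binomial counts, P(miss) = P(X₁ ≤ c) × P(X₂ ≤ c), where X ~ Bin(218, p), c = 21 for any grade and c = 2 for serious or Grade 3 to 5.

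| Type of term | True rates | Calculation | P(miss) |
|---|---|---|---|
| Any grade | 6% vs 3% | 0.988 × 1.000 | 99% |
| Any grade | 8% vs 4% | 0.845 × 1.000 | about 84% |
| Any grade | 9% vs 9% | 0.681 × 0.681 | 46% |
| Any grade | 12% vs 8% | 0.166 × 0.845 | 14% |
| Serious or Grade 3 to 5 | 1% vs 0.5% | 0.628 × 0.903 | 57% |
| Serious or Grade 3 to 5 | 2% vs 1% | 0.187 × 0.628 | 12% |
| Serious or Grade 3 to 5 | 3% vs 1% | 0.040 × 0.628 | 2.5% |
| Serious or Grade 3 to 5 | 5% vs 2% | 0.001 × 0.187 | below 0.1% |

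The gap is wide for any-grade terms below 10% and small for severe terms at about 2% or more in one arm.

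**3. What one term can hide.** A term seen in 21 vs 5 participants (9.6% vs 2.3%) stays in Tier 3. The Miettinen-Nurminen interval that would not be shown is 7.3 points (3.1 to 12.3).

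**4. What pooling could add.** Assumed any-grade counts, pembrolizumab vs placebo: radiation pneumonitis 20 vs 17 (9.2% vs 7.8%) and pneumonitis 17 vs 4 (7.8% vs 1.8%). Both terms are below 22, so both are Tier 3. The pooled count depends on how many participants have both. The interval is the set of δ with |(p₁ − p₂ − δ)/√V(δ)| ≤ 1.96, where V(δ) = [p̃₁(1 − p̃₁)/n₁ + p̃₂(1 − p̃₂)/n₂] × N/(N − 1), N = n₁ + n₂, and the p̃ are the maximum likelihood estimates under p̃₁ − p̃₂ = δ.

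| Overlap | Pooled counts | Rates | Difference (95% CI), points |
|---|---|---|---|
| None | 20 + 17 = 37 vs 17 + 4 = 21 | 17.0% vs 9.6% | 7.3 (1.0 to 13.9) |
| 3 in the pembrolizumab arm | 37 − 3 = 34 vs 21 | 15.6% vs 9.6% | 6.0 (-0.3 to 12.4) |
| Full | 20 vs 17 | 9.2% vs 7.8% | 1.4 (-4.0 to 6.8) |

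The per-term tables are the same in all three rows, so they cannot tell these cases apart. With full overlap even the pooled rate stays under 10%, so a grouped row left to the frequency rule could also end in Tier 3.

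**5. How typical this illustration is.** If these counts were the true rates, both terms would miss 10% with probability 0.648 × 0.871 × 0.871 × 1.000 = 0.49, treating terms and arms as independent.

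**The case against.** The strongest reply is that the plan already covers the cases that matter most. Three serious or Grade 3 to 5 cases of one term in one arm trigger a CI. A reader who saw only the 10% rule might infer that pneumonitis could go without any between-arm comparison. The documents do not support that reading, because the 1% rule will usually catch severe terms. Nor is an excess concealed: Tier 3 still prints each arm's percentage, so 7.8% vs 1.8% would be visible. This stands, and it limits the point to the pooled count and to any-grade terms below 10%. Subtracting percentages still gives no interval, and adding terms counts some participants twice.

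A reader might also infer that the reason given for an empty Tier 1 is unsound because dosing here differs from the cited experience. Section 8.1.8.1.1 does say: "The first dose of pembrolizumab or placebo should be administered prior to start of SBRT". But of the two cited studies in metastatic disease, one gave pembrolizumab after SBRT and the other, by its title in Section 11, gave it concurrently. Poor pulmonary function appears in Section 8.1.4 as one possible reason for inoperability, without a frequency. The documents do not show the rationale to be wrong, and a descriptive Tier 2 row does not need it to be.

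System organ class rows do not close the gap. The text of 9.6.2 tiers them by frequency while Table 9 lists them under Tier 3, which should be reconciled, but such a row would not isolate pneumonitis in any case.

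Finally, the supplemental SAP may already hold a grouped analysis. Section 9 allows it to carry changes to non-confirmatory analyses, so this cannot be excluded, although 9.6.2 does not refer to it.

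**Conclusion.** The point holds in a limited form. No pooled pneumonitis comparison is prespecified. Any-grade terms under 10% in both arms get per-arm rates only, and severe terms are usually compared, but one at a time. At 218 per arm an any-grade term is left without a CI about 84% of the time at true rates of 8% vs 4%, and 99% at 6% vs 3%. What pooling would show depends on overlap: 7.3, 6.0 or 1.4 points in the illustration, with only the first interval excluding zero.

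This rests on three assumptions: about 218 treated per arm; assumed event rates and counts, since the documents give none; and coding of radiation pneumonitis, pneumonitis and related lung conditions as separate terms. The last is inferred from the tiering by specific term, because the dictionary is not named. That pneumonitis is the toxicity to single out is also an inference, from Sections 6.5, 6.6 and 7.1 and exclusion criterion 9.

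Priority is low. The recommendation to stop has been made, the Tier 2 intervals are labelled descriptive, and only the clarity of the safety report is affected.

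**What to change.** In Section 9.6.2 and Table 9, or in the supplemental SAP as Section 9 allows, add one grouped parameter, *pneumonitis of any cause*:

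- List the dictionary terms it contains (pneumonitis, radiation pneumonitis, interstitial and immune-mediated lung disease). Fix and date the list before the end-of-study safety analysis, and record its timing relative to unblinding.
- Count each participant once, in the APaT population.
- Report the Miettinen-Nurminen difference and 95% CI for any grade, Grade 3 to 5, and serious or fatal events, whatever the observed frequency. Label them descriptive.

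Keep the per-term rows. The Tier 1 statement need not change.

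The cost is a term list and a few table rows from data already collected. The downside is a few more unadjusted intervals among those that 9.6.2 already treats as descriptive.

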9.6.3 Analysis Methods for PRO Endpoints

A constrained longitudinal data analysis (cLDA) model will be applied for each endpoint, with the PRO score as the response variable, and treatment, time, treatment by time interaction, and clinical study stratification factors as covariates. Least square mean change from baseline will be summarized for each outcome. The difference in the least square mean change from baseline will be reported at the primary analysis time point.

Descriptive analyses will assess the empirical mean change (with 95% CIs) from baseline across all time points for the Global health status/QoL (QLQ-C30 items 29, 30), cough (QLQ-LC13 item 1), chest pain (QLQ-LC13 item 10), and dyspnea (QLQ-LC13 item 8) scores.

The number and proportion of patients who "improved", "remained stable", or "deteriorated" from baseline will be summarized.

Details of additional PRO analyses will be included in the sSAP.

9.6.4 Demographic and Baseline Characteristics

The comparability of the treatment groups for each relevant demographic and baseline characteristic will be assessed by the use of tables and/or graphs. No statistical hypothesis tests will be performed on these characteristics. The number and percentage of participants screened and randomized and the primary reason for screening failure and discontinuation will be displayed. Demographic variables, baseline characteristics, primary and secondary diagnoses, and prior and concomitant therapies will be summarized by treatment either by descriptive statistics or categorical tables.

